2.4. STUDY SITE PARTICIPATION

This study will require a minimum of two participating sites. Each site will have a sufficient patient population to enroll 20-30 subjects over the enrollment period (3 months). Each site must have sufficient transbronchial biopsy volume (defined as at least 100 cases per year). To ensure adequate access to patients across the various indications for transbronchial biopsy, each site must have institutional centers for Lung Cancer, Lung Transplantation and Interstitial Lung Disease. In addition, the principal investigator and each participating co-investigator at each site must have cryobiopsy experience, defined as completion of at least 10 cryobiopsies.

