3.7.6. SERIOUS ADVERSE EVENT REPORTING

A Serious Adverse Event is defined as the occurrence of bleeding grade ≥ 3 (see Adverse Events for bleeding grading system), pneumothorax requiring chest tube placement (Grade ≥ 2 , see Adverse Events for pneumothorax grading system), post-procedure respiratory failure defined as the need for non-invasive or mechanical ventilation requiring ICU admission, or death, which have occurred within 30 days after procedure, respectively.

All device and/or procedure related adverse events will be reported. Device related events will be collected from initiation of the index procedure (insertion of the cryoprobe into the working channel of the bronchoscope), intra-procedure, and during the standard of care follow-up period of 30 days. 30 day follow up will be assessed by chart review, if data is not able to be extracted by chart review a phone call will be made to assess any adverse events that may have occurred. Study sites are responsible to report adverse events and complications to their IRBs according to institutional requirements.

The study clinician at the site will complete a SAE Form within the following timelines:

- All deaths and immediately life-threatening events, related to the device or the procedure will be recorded on the SAE Form and submitted to the DSMB/study sponsor, lead coordinating center, and device manufacturer within 24 hours of site awareness.
- Other SAEs will be submitted to the DSMB/study sponsor and lead coordinating center within 72 hours of site awareness.

All SAEs will be followed until satisfactory resolution or until the site investigator deems the event to be chronic or the adherence to be stable. Other supporting documentation of the event may be requested by the DSMB/study sponsor and should be provided as soon as possible. The study sponsor will be responsible for notifying FDA of any unexpected fatal or life-threatening suspected adverse reaction as soon as possible but in no case later than 7 calendar days after the sponsor's initial receipt of the information.

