5. STATISTICAL CONSIDERATIONS

5.1. STATISTICAL AND ANALYTICAL PLANS

The study is not powered to make a statistical conclusion due to the small sample size and the safety phase in which the treatment is. As the true safety profile of the 1.1mm flexible single-use cryoprobe with oversheath is not known, we will base our statistical plan based on current standard method for transbronchial biopsy, forceps biopsy.

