5.4.2. ANALYSIS OF THE PRIMARY SAFETY ENDPOINT

The primary endpoint is the incidence of serious adverse events defined as occurrence of bleeding grade ≥ 3 (see Adverse Events for bleeding grading system), pneumothorax requiring chest tube placement (Grade ≥ 2 , see Adverse Events for pneumothorax grading system), post-procedure respiratory failure defined as the need for non-invasive or mechanical ventilation requiring ICU admission, or death, which have occurred within 30 days after procedure, respectively. The incidence will be calculated as the proportion of patients in whom a serious adverse event occurred divided by those who underwent the index procedure (insertion of the cryoprobe into the working channel of the bronchoscope).

As the true safety profile of the 1.1mm flexible cryoprobe with oversheath is not currently known, and no standard minimally significant difference in a combined bleeding and pneumothorax outcome (such as in this study) is known, we will use currently available literature on a comparable biopsy method, (forceps biopsy and the larger 1.9mm and 2.4mm cryoprobes).

Based on review of the published literature (**Table 1**), we conservatively estimate the current combined bleeding and pneumothorax proportion to be 30% for transbronchial biopsy in standard practice. The procedure will be considered safe if the final proportion of serious adverse events is 30% or less. This will infer a standard of safety for the 1.1mm flexible single-use cryoprobe with oversheath comparable to current transbronchial biopsy standard of care.

Table 1: Literature review of bleeding and pneumothorax rates

Author	Definition of bleeding as per study	Number of patients in CBx, n (%)	Number of patients in FBx, n (%)
Aktas et al. (2010) ¹³ , (n = 41); All performed CB and FB; CB = 41, FB = 41	No bleeding Simultaneous bleeding Mild: cold water + adrenaline Moderate: APC application Severe : hemodynamic compromise Pneumothorax	26 (63.4) 5 (12.2) 8 (19.5) 2 (4.9) 0 (0) not reported	27 (65.9) 5 (12.2) 9 (21.9) 0 (0) 0 (0) not reported
Hetzell et al. (2012) ¹⁴ , (n = 593); CB = 296, FB = 297	No bleeding Mild: suctioning Severe: ice cold saline, diluted vasoconstrictive drug, balloon tamponade, APC, MV, conversion to rigid bronchoscope. Pneumothorax	59 (19.9) 183 (61.8) 54 (18.2) not reported	91 (30.6) 153 (51.5) 53 (17.8) not reported

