5.7. SAMPLE SIZE

This is a safety study. The goal of this study is to identify any high frequency adverse events, as well as collect preliminary data on the potential efficacy of the novel 1.1mm flexible single-use cryoprobe with oversheath. As no current data exists to accurately estimate the variance in SAE rates, there is no reliable data to power this study. We conservatively estimate that a stable estimation will of the SAE rate will occur after 50 cases. Thus in this initial study, we will include 50 participants.

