6. MEASURES TO MINIMIZE BIAS: ENROLLMENT/RANDOMIZATION/MASKING PROCEDURES

Participants will be enrolled at each institution participating in the study on a referral basis to interventional pulmonology. Due to the nature of the study, patients and bronchoscopists will not be blinded. The treating bronchoscopist will be the outcome assessor.

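### Day-30 follow-up relies on the site chart, with a call only when the chart fails, so serious adverse events treated elsewhere may be missed and would then count as event-free

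*Combined protocol and SAP*

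**What the plan says.** The primary endpoint (sections 2.2 and 5.4.2) is a 30-day composite: bleeding of grade 3 or higher, pneumothorax needing a chest tube, respiratory failure leading to ICU care, or death. Section 3.7.6 collects what happens after discharge during standard-of-care follow-up. The chart is the first source, and "if data is not able to be extracted by chart review a phone call will be made". No study visit or routine contact is described.

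On the source of patients, section 6 says: "Participants will be enrolled at each institution participating in the study on a referral basis to interventional pulmonology". The same section makes the unblinded treating bronchoscopist the outcome assessor.

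In section 5.4.2 the patients with an SAE are "divided by those who underwent the index procedure (insertion of the cryoprobe into the working channel of the bronchoscope"). The decision rule there is: "The procedure will be considered safe if the final proportion of serious adverse events is 30% or less".

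**The concern.** The call depends on the chart being unusable, and the plan does not say what that means. A chart that is plainly empty would presumably prompt a call. A chart that has later entries and records no complication may look usable even though the patient was admitted to another hospital. The back-up is weakest in that case, because nothing signals that anything is missing.

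The denominator then settles how such a patient is counted. Everyone who had the index procedure is included, whether or not day-30 status was verified, so a patient with an unseen event adds to the denominator and not to the numerator. The error runs one way, toward a lower SAE proportion and a verdict of safe. Estimating that proportion is also the first aim in section 5.2, so a low bias matters even when the verdict is not in doubt. Sections 3.9 and 5.6 pause enrolment after any SAE for review by the DSMB, and an SAE that nobody sees triggers no review.

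**Working it through.** **Inputs from the plan.** The sample size is 50 (section 5.7: "Thus in this initial study, we will include 50 participants"). The plan gives no alpha, power, alternative rate or precision target, and says "there is no reliable data to power this study", so 50 can be neither reproduced nor refuted. The safety limit is 30%, and 0.30 × 50 = 15, so at most 15 events pass and 16/50 = 32% does not.

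**Input not in the plan.** The fraction m of all SAEs that goes unrecorded is an assumption, taken from 0% to 30%.

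**Step 1: which components are exposed.**

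| Component | How it is normally seen | Exposed to the chart rule? |
|---|---|---|
| Bleeding, grade 3 or higher | Grade 3 is defined by inflating a bronchial blocker (section 3.7.5), ordinarily an act during the procedure | Little |
| Pneumothorax with chest tube | X-ray after every procedure (section 3.4); x-ray and ultrasound documentation (section 3.7.5) | Only if delayed |
| Respiratory failure with ICU admission | Any time to day 30 | Yes, after discharge |
| Death | Any time to day 30 | Yes, after discharge |

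**Step 2: effect on the count (illustration).** Two missed events give:

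- 17/50 = 34% becomes 15/50 = 30%, and the verdict changes.
- 5/50 = 10% becomes 3/50 = 6%, and the verdict stays but the estimate falls by 4 percentage points.

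**Step 3: chance of meeting the criterion.** If p is the true SAE rate and events are independent, the recorded count is binomial with n = 50 and probability p(1 − m). The table gives P(count ≤ 15).

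| True rate p | m = 0% | m = 10% | m = 20% | m = 30% |
|---|---|---|---|---|
| 10% | about 100% | about 100% | about 100% | about 100% |
| 20% | 96.9% | 98.8% | 99.6% | 99.9% |
| 30% | 56.9% | 74.3% | 87.5% | 95.4% |
| 35% | 28.0% | 47.7% | 68.8% | 85.7% |
| 40% | 9.6% | 23.3% | 44.7% | 68.8% |

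**Step 4: dilution.** Only part of the composite is exposed, so the overall loss is smaller than the loss among exposed events. If 25% of SAEs are exposed and half of those are missed (both assumed), m = 0.25 × 0.5 = 12.5%. A true 40% is then recorded as 0.40 × 0.875 = 35% on average, and passes 28.0% of the time instead of 9.6%.

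**Step 5: what a worst-case bound would show.** With x recorded events and u event-free patients of unconfirmed status, the bound is (x + u)/50. For x = 5, u = 2 gives 7/50 = 14% and u = 5 gives 10/50 = 20%, against a recorded 10%.

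**Step 6: a minor inconsistency in duration.** The synopsis gives a study duration of 3 months and 30 days per participant. Section 2.4 asks each site for a "sufficient patient population to enroll 20-30 subjects over the enrollment period (3 months"). Three months of enrolment plus 30 days for the last patient is about 4 months, so the two statements need to be reconciled.

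**The case against.** The best defence is that section 3.7.6 is undefined rather than wrong. A chart with no day-30 information can fairly be read as one from which data cannot be extracted, and the call would then be made. The plan also has other checks: central review of all endpoint data (section 4), queries on missing or anomalous data (section 8), and documented contact attempts for patients lost to follow-up (section 2.8). Referral may be internal, and each site must have lung cancer, transplant and interstitial lung disease centers (section 2.4), so many patients may be followed at the site. Finally, section 5.1 says: "The study is not powered to make a statistical conclusion due to the small sample size".

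Much of this stands, and it rules out some stronger readings:

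- A reader might infer that the plan records SAEs treated elsewhere as no event. No section contains such a coding rule. It is a possible result of the call condition and the denominator together.
- A reader might infer that patients treated in the last month would lack full follow-up. No section closes the study at 3 months, and the endpoint definition requires 30 days throughout.
- A reader might add delayed haemoptysis to the events at risk. Bleeding counts toward the endpoint only at grade 3 or 4, and grade 3 is defined by an act that ordinarily belongs to the procedure.

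The defence does not close the gap. A plausible but mistaken entry of no SAE is neither missing nor anomalous, so a data query would not find it. The loss-to-follow-up procedure covers patients known to be lost. Central review can check only what the site has recorded. Being unpowered does not help either, because section 5.4.2 still declares the procedure safe or not on the observed proportion.

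**Conclusion.** The concern holds as a risk of under-ascertainment whose direction is known and whose size is not. It affects mainly delayed pneumothorax needing a tube, respiratory failure with ICU admission, and death. It rests on three features of the text: a conditional call with an undefined trigger, a denominator of all index procedures, and no rule for unknown day-30 status. It also assumes that some patients receive later care outside the site. Enrolment by referral makes that plausible, but the documents do not quantify it.

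The verdict of safe is sensitive only if the true rate is near or above the 30% limit. At about 10% or less the trial passes whatever is missed, and the harm is a reported rate that is too low. Analysis cannot recover an outcome that was never ascertained, so the remedy belongs in data collection.

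**What to change.** In section 3.7.6, require a day-30 contact, with the patient or a contact the patient has named, for everyone who had the index procedure. Keep chart review as a supplement. Where a contact reports care elsewhere, request that record so that the event can be classified.

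Add one CRF field stating whether day-30 status was confirmed by contact, by chart only, or is unknown.

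In section 5.4.2, state how unknown status is handled. Report the SAE proportion on the index-procedure denominator alongside a worst-case analysis that counts patients with no recorded SAE and unconfirmed status as events. Show how many of these are chart-only and how many are unknown.

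In the synopsis, reconcile the study duration with the enrolment period plus 30-day follow-up.

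The cost is at most 50 short calls by existing coordinators and one CRF field, plus a record request where a call reports outside care. The change concerns measurement only and does not affect treatment.

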3.8. SAFETY OVERSIGHT

Safety oversight will be under the direction of a DSMB composed of individuals with the appropriate expertise, including interventional pulmonology. Out of an abundance of caution, the DSMB will meet to review cases and assess safety after each 10 consecutive patients have been enrolled (cases will be consecutively batched in groups of 10). The DSMB will operate under the rules of an approved charter that will be written and reviewed at the organizational meeting of the DSMB. At this time, each data element that the DSMB needs to assess will be clearly defined.

Proposed DSMB members:

[name]: DSMB Chair, Pulmonary and Critical Care, Medical University of South Carolina

[name]: Interventional Pulmonary, Duke University

[name], Division Chief, Pulmonary and Critical Care, Johns Hopkins University

[name], Interventional Pulmonary, University of Pittsburgh

[name], Pulmonary and Critical Care, University of Pennsylvania

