Safety of a Sheath Cryoprobe Bronchoscopic Transbronchial Biopsy Technique

NCT04486560

Document Creation Date: October 1, 2020

Safety of a Sheath Cryoprobe Bronchoscopic Transbronchial Biopsy Technique
ACRONYM : FROSTBITE

Principal Investigator: [name]

Draft or Version Number: v.0.8
01 Oct 2020

STATEMENT OF COMPLIANCE

The trial will be conducted in accordance with the ICH GCP E6, the Code of Federal Regulations on the Protection of Human Subjects (45 CFR Part 46), and the STTR Terms of Award. The Principal Investigator will assure that no deviation from, or changes to the protocol will take place without prior agreement from the sponsor and documented approval from the Institutional Review Board (IRB), except where necessary to eliminate an immediate hazard(s) to the trial participants. All personnel involved in the conduct of this study have completed Human Subjects Protection Training.

I agree to ensure that all staff members involved in the conduct of this study are informed about their obligations in meeting the above commitments.

Principal Investigator: _____

Print/Type Name

Signed: _____ Date: _____

Signature

STUDY CONTACT INFORMATION

Coordinating Center	Core Lab

Johns Hopkins University
 
Principle Investigator (Lead PI):
 
[name], DO Associate Professor of Medicine Johns Hopkins University [contact] Email: [contact]
 
Research Coordinator:
 
[name] Research Program Manager [contact] Email: [contact]
	
Pathology: [name] Associate Professor of Pathology Johns Hopkins University [contact]
 
Radiology: [name] Associate Professor of Radiology Johns Hopkins University [contact]

Additional Site Contact	

[name] Associate Professor of Medicine Vanderbilt University [contact] Email: [contact]
	

PROTOCOL SYNOPSIS

Title:	Safety of a Sheath Cryoprobe Bronchoscopic Transbronchial Biopsy Technique (The FROSTBITE Trial)
Study Objective:	To determine the safety profile of a 1.1mm flexible single-use cryoprobe with oversheath used for transbronchial lung biopsy via a bronchoscopic approach
Study Device:	ERBE 1.1mm flexible single-use cryoprobe with oversheath
Design:	A multi-center, non-randomized, single-arm, prospective trial designed to determine the safety profile of a novel cryoprobe and generate preliminary efficacy data.
Phase:	Post-Market
Number of Sites enrolling participants:	2
Number of Subjects:	50
Study Participant Duration:	30 days
Study Duration:	3 months

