3.9. STUDY HALTING RULES

Any SAE will serve as a stopping rule. The DSMB will convene to adjudicate the event. Enrollment will resume if the SAE is adjudicated by the DSMB. Additionally, if the SAE rate rises above 30% for two consecutive batches (10 cases per batch), the study will be halted.

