4. CLINICAL MONITORING

Clinical site monitoring is conducted to ensure that the rights and well-being of human subjects are protected, that the reported trial data are accurate, complete, and verifiable, and that the conduct of the trial is in compliance with the currently approved protocol/amendment(s), with GCP, and with applicable regulatory requirement(s).

- Monitoring for this study will be performed by Johns Hopkins University
- Centralized, initial assessments and monthly assessments, and comprehensive review of all primary and secondary endpoint data.

- Details of clinical site monitoring are documented in a CMP. The CMP describes in detail who will conduct the monitoring, at what frequency monitoring will be done, at what level of detail monitoring will be performed, and the distribution of monitoring reports.
- Independent audits will be conducted by Johns Hopkins University to ensure monitoring practices are performed consistently across all participating sites and that monitors are following the CMP.

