12. CONFLICT OF INTERESTS POLICY

The independence of this study from any actual or perceived influence, such as by medical device industry, is critical. Therefore any actual conflict of interest of persons who have a role in the design, conduct, analysis, publication, or any aspect of this trial will be disclosed and managed. Furthermore, persons who have a perceived conflict of interest will be required to have such conflicts managed in a way that is appropriate to their participation in the trial. The study leadership has established policies and procedures for all study group members to disclose all conflicts of interest and will establish a mechanism for the management of all reported dualities of interest.

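### The proposed DSMB is not fully independent of the lead site: one of its five members is a division chief at the institution that coordinates, enrols in and monitors the trial

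*Combined protocol and SAP*

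**What the plan says.** Section 3.8 puts safety oversight under a DSMB and gives a list headed "Proposed DSMB members". It has five entries. The chair is described as "DSMB Chair, Pulmonary and Critical Care, Medical University of South Carolina", and three further members are at Duke, Pittsburgh and Pennsylvania. The remaining entry is "Division Chief, Pulmonary and Critical Care, Johns Hopkins University".

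The study contact page gives Johns Hopkins as the coordinating centre and the lead investigator's institution, with Vanderbilt as the additional site. Section 4 assigns monitoring to Johns Hopkins.

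Under 3.9 any SAE stops the study, and "The DSMB will convene to adjudicate the event". Enrolment resumes once that has been done, and 5.6 repeats this for all sites. Section 5.5 makes the SAE rate after each ten completed cases available only to the DSMB.

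On safeguards, 3.8 refers to an "approved charter that will be written and reviewed at the organizational meeting of the DSMB". Section 12 says "The independence of this study from any actual or perceived influence, such as by medical device industry, is critical" and sets out a general policy that conflicts are to be disclosed and managed.

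**The concern.** This is a single-arm, unblinded study in which the treating bronchoscopist assesses the outcome (section 6). A board outside the institutions running the trial is a main safeguard on whether it should continue after a serious event. Here one of the people proposed for that task holds a senior post at the institution leading the trial. That institution has an interest in the trial continuing and in how its own site's events are viewed.

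Membership matters more than usual because the restart rule gives the board nothing to measure an event against. It says that adjudication must happen, but not what finding would allow or prevent resumption. When a decision rests on judgement, the protection lies in who makes it. At stake are patient protection during enrolment and the credibility of the oversight when the SAE rate is reported.

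**Working it through.** The plan gives no figure to reproduce on this point. The check sets the sections side by side, with a small calculation of how many decisions rest on the board's judgement.

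1. **Roles of the lead institution.** Johns Hopkins is the coordinating centre, the lead investigator's institution and the home of both core laboratories (study contact page), the monitor (section 4) and the holder of the data (10.3). It is also an enrolling site: the synopsis counts two, and the contact page, 3.6 and 9.2 identify only Johns Hopkins and Vanderbilt.

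2. **Composition of the board.** Members from an enrolling or coordinating institution: 1/5 = 20%. External members, including the chair: 4/5 = 80%. Vanderbilt has no seat, so the only affiliated seat belongs to the lead site.

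3. **Share of patients from that member's institution.** Section 2.4 expects each site to be able to enrol 20 to 30 patients. If that range holds, 20/50 = 40% to 30/50 = 60%.

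4. **How much is left to judgement.** The one numeric rule (3.9) halts the study if the SAE rate is above 30% in two consecutive batches of ten. Read batch by batch, that means at least 4 of 10 twice, or at least 8 SAEs in 20 patients. Every other resumption depends on the board's adjudication. Assume independent patients, a common true rate p, and at most one SAE per patient. Let q = P(X ≥ 4) with X ~ Binomial(10, p). Over five batches,

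 P(numeric halt) = 1 − [(1−q)^5 + 5q(1−q)^4 + 6q²(1−q)³ + q³(1−q)²].

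| True SAE rate p (assumed) | q | P(numeric halt) | Expected SAEs if all 50 treated, 50p | Of these, at Johns Hopkins (40% to 60%) |
|---|---|---|---|---|
| 10% | 0.013 | 0.001 | 5 | 2 to 3 |
| 20% | 0.121 | 0.053 | 10 | 4 to 6 |
| 30% | 0.350 | 0.352 | 15 | 6 to 9 |
| 40% | 0.618 | 0.764 | 20 | 8 to 12 |

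 For p = 20%: q = 0.1209, so 1 − (0.5250 + 0.3610 + 0.0596 + 0.0014) = 0.053. At that rate the numeric rule would act in about one trial in twenty, while about ten restart decisions would rest on judgement, four to six of them for events at Johns Hopkins. The 30% row corresponds to the most SAEs compatible with the plan's own criterion for calling the procedure safe (0.30 × 50 = 15). The 40% row shows that the numeric rule does act at clearly high rates, although the expected count there overstates what would be seen because the trial would often stop early. The table counts decisions. It does not measure bias.

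5. **Safeguards in the text.** No section states a DSMB independence requirement, a quorum, a voting rule or a recusal rule. Section 12 is general and does not mention the DSMB. The charter is still to be written, and nothing in 3.8 says that it must deal with this seat.

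**The case against.** Much can fairly be said against making more of this.

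- The list is only proposed and the charter is unwritten, so recusal may yet be provided for. This stands. It makes the point one about a proposal, and it is also why the change is easy now.
- Four of five members, including the chair, are external. This stands too. The board as a whole cannot be called dependent on the lead site.
- Section 12 covers anyone with a role in any aspect of the trial, so it reaches DSMB members. That is correct, but it does not say how this particular tie is to be managed.
- SAE forms already go to the lead coordinating centre (3.7.6), so that centre could count events for itself. This weakens the point about interim data. It leaves the points about adjudication and restart untouched.

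Several stronger readings are tempting, and the documents do not support them.

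- A reader might infer that this member would help decide the primary endpoint, because the SAE definition in 3.7.6 has the same components as the endpoint in 5.4.2. But section 6 names the treating bronchoscopist as outcome assessor, and no section says that DSMB adjudication sets or overrides the classification that is analysed.
- A reader might infer that the division chief supervises the lead investigator. The contact page says only "DO Associate Professor of Medicine Johns Hopkins University" and gives no division or reporting line.
- Voting is not described anywhere, so calling this member a voting member is an assumption.
- A reader might take section 4 ("Independent audits will be conducted by Johns Hopkins University") as a second failed check on the same decisions. Those audits concern monitoring practice and have no role in DSMB adjudication.
- Nor is outside scrutiny absent: there are the external members, the sites' IRBs, sponsor notification to FDA of certain events (3.7.6) and possible regulatory inspection (section 8).

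**Conclusion.** The point holds in a limited form. The proposed board is not fully independent of the lead site: one seat in five belongs to a division chief at the institution that coordinates, enrols in and monitors the trial. The board reviews every SAE, decides on resumption without a stated criterion, and is the designated recipient of the interim SAE rate. Nothing in the protocol requires this tie to be managed by recusal or replacement.

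The size is 1 of 5 members. The 40% to 60% share of patients rests on the site capacity in 2.4, and it describes exposure, not influence. The table rests on assumed SAE rates and independent patients. The documents give no basis for estimating a bias, and they do not show that any decision would come out differently. The case for acting is that the weakness lies in the plan as written, it touches every restart decision, and it costs almost nothing to remove.

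**What to change.** In 3.8, require that DSMB members who take part in SAE adjudication, restart decisions or interim review come from institutions that neither enrol patients in nor coordinate the trial. Then either replace the Johns Hopkins seat with an external member, or keep it as a non-voting seat recused from those decisions and from the interim data. The charter should carry the same rule when it is written.

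The best time is before the organizational meeting, while the membership is still only proposed. Replacement costs a short delay to appoint someone. Recusal costs one fewer adjudicating member, leaving four. Neither adds patients, procedures or analyses.
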